10.2.2.2 Close Observation

- Repeat liver enzyme and serum bilirubin tests two or three times weekly. Frequency of re-testing can decrease to once a week or less if abnormalities stabilize or the trial drug has been discontinued and the patient is asymptomatic
- Obtain a more detailed history of symptoms and prior or concurrent diseases

- Obtain a history of concomitant drug use (including non-prescription medications and herbal and dietary supplement preparations), alcohol use, recreational drug use, and special diets
- Consider ruling out alternate etiology including acute viral hepatitis types A, B, C, D, and E; autoimmune or alcoholic hepatitis; non-alcoholic steatohepatitis; hypoxic/ischemic hepatopathy; and biliary tract disease
- Obtain a history of exposure to environmental chemical agents
- Obtain additional tests to evaluate liver function, as appropriate (e.g., INR, direct bilirubin)
- Consider gastroenterology or hepatology consultations
- Follow subjects with potential drug-induced liver injury (DILI) until the laboratory, and new associated clinical abnormalities have normalized or returned to baseline (enrollment) values or have stabilized (defined as laboratory values being stable for 3 months). Continue to work up for alternate etiologies for the abnormal liver disease as stated above until case has resolved. If imaging changes are found as part of the assessment for etiology, these should be continued to be followed until normalization or returned to baseline or until the investigator feels the changes have stabilized.

10.2.2.3 De-challenge/Re-challenge for Liver and Clinical Hepatitis Monitoring

1. Re-challenge is not recommended:
 - a) If a patient has had possible/probable drug-induced liver injury
 - b) If a decompensation event has occurred (i.e., variceal hemorrhage, ascites, hepatic encephalopathy, etc.).
2. If the event is assessed as due to underlying cholestatic liver disease variability or another alternative etiology is identified AND liver tests returned to baseline, re-challenge may be considered after consultation with the sponsor Medical Monitor.
3. If the ALT/total bilirubin elevations are observed after re-challenge, then repeat re-challenge is discouraged.

If a patient is permanently discontinued, monitoring should be continued as outlined in [Section 10.2.2.8](#).

10.2.2.4 Diarrhea

Study drug should be discontinued if a patient develops diarrhea with at least 1 of the following concomitant signs or symptoms: grossly bloody stools, vomiting, dehydration requiring treatment with oral or intravenous rehydration and/or electrolyte imbalances, fever ($\geq 38^{\circ}\text{C}$) and/or the diarrhea persists for 7 or more days. Patients with prolonged diarrhea (≥ 7 days) should be assessed using hemoccult cards.

Blood in stools or any other signs of bleeding should trigger clinical and laboratory assessment such as measurement of PT/aPTT, INR, platelets, etc. Any deficits should be corrected, as clinically indicated.

Cause of bleeding should be investigated, and an evaluation should be obtained. If there is a reduction in hemoglobin greater than 2 g/dL there should be a discussion with the Medical Monitor and the appropriate work up will be decided. Information needed for this discussion should include presence of any diarrhea, recent iron studies, any signs of gross bleeding and what organs are involved, recent and current complete blood count, INR, any changes in heart rate, blood pressure, weight, last results of imaging and endoscopy/ colonoscopy and recent infectious work up, if done.

If gross blood in stool/bleeding is seen, an AE of blood in stool/bleeding should be reported.

Study drug will be reintroduced (re-challenge) when the symptoms have resolved. If the diarrhea re-occurs within 1 week after the re-challenge with no alternate etiology, the patient will be permanently discontinued and monitored as outlined in [Section 10.2.2.8](#).

10.2.2.5 Fat-soluble Vitamin Deficiency

Queries related to TEAEs indicative of end-organ damage, i.e., impaired hepatic synthetic function presenting as e.g., bone fracture/rickets, GI or other organ bleeding/ecchymosis or night blindness, will be issued when a patient presents with worsening of fat-soluble vitamin deficiency (see [Section 10.2.1](#) for monitoring fat-soluble vitamin levels by laboratory assessments). Treatment should be discontinued in patients with evidence of end-organ damage due to fat-soluble vitamin deficiency.

10.2.2.6 Treatment-emergent Iron Deficiency Anemia

Events of iron deficiency anemia are identified as part of TEAE reporting and hematology assessments. Patients will be evaluated for fecal blood loss if they present with:

- A decrease in hemoglobin of ≥ 2 g/dL
- A report of blood in stool; if so, a further diagnostic work up will be performed, following confirmation of blood in stool with hemoccult cards.

Patients will be managed per institutional standard of care with iron supplementation.

10.2.2.7 Re-challenge after Discontinuation/Interruption of Study Drug

The DSMB will evaluate the safety data for patients who have discontinued study drug for an extended period on a case-by-case basis to determine whether re-challenge with A4250 is appropriate. The minimal duration of the discontinuation should be at least one to two weeks.

Patients that have discontinued for an extended period and allowed re-challenge by DSMB will use the last labs prior to restart as the new baseline for determining if DILI criteria are met.

10.2.2.8 Monitoring after Permanent Discontinuation of Study Drug Due to Safety

Once study drug is permanently discontinued for liver, hepatitis, diarrhea, or other severe AE related to study drug, the patient will be monitored weekly until the laboratory and clinical parameters have normalized/stabilized.

10.2.3 Demographics/Medical and Surgical History (For Cohort 2 only)

Demographic information per country regulations, along with medical and surgical history, will be obtained and recorded in the eCRF at Visit S-1.

Medical and surgical history will be entered in the eCRF at Visit S-1. This includes date of diagnosis of PFIC, prior investigational medications for PFIC, historical (3 months prior to Screening, and up to 5 years prior to Screening for BRIC) hepatic biochemical parameters (e.g., AST, ALT, and total bilirubin), ongoing medication, any surgery performed, any other diagnosis, and historical biopsy data.

For patients with BRIC, information on flares will be collected, including frequency, duration, and severity of flares within the last 6 months at a minimum, and within the last 5 years, if possible. A flare/cholestatic episode can be self-reported or clinically assessed based on medical history. Clinical signs and symptoms during a cholestatic episode/flare can include nausea, vomiting and pruritus followed by jaundice, fatigue, weight loss, malaise, steatorrhea, night blindness. Increased bilirubin and alkaline phosphatase levels and increased INR can be observed. ALT, AST and GGT can be normal to mildly elevated.

If a liver biopsy has been performed within 1 year prior to Screening, or during the study, the results will be recorded in the eCRF.

10.2.4 Clinical Genetic Testing (For Cohort 2 only)

For previous confirmatory clinical genetic testing results for PFIC, including BRIC, Type performed prior to Screening Visit S-1, the confirmatory clinical genetic testing laboratory report will be verified to determine eligibility.

If the historical clinical genetic result is equivocal, unavailable, or unobtainable, clinical genetic analysis will be performed to confirm pathologic biallelic variations of the *ATP8B1*, *ABCB11* *ABCB4*, *NR1H4*, *TJP2*, *DCDC2*, *CLDN1*, and *MYO5B* genes and verified to determine eligibility. No other diagnostic genetic testing will be offered.

10.2.5 Physical Examination

A physician or suitably trained qualified assistant will perform a complete physical examination, including a skin examination, at Visits S-1, 1, 3, 5, 8, and 11.

A complete physical examination will include assessment of general appearance, eyes, ears, nose, throat, head/neck/thyroid, lymph nodes, cardiovascular, lungs/chest, abdomen, genitourinary, extremities, skin, musculoskeletal, neurologic, and other. An abbreviated

physical examination will include general appearance, cardiovascular, abdomen, and other assessments based on patient status.

Skin will be thoroughly examined and excoriations/scratch marks recorded.

10.2.6 Vital Signs

Evaluation of vital signs will be performed at all visits. This includes blood pressure (systolic and diastolic), pulse, respiratory rate, temperature, height/length (using certified stadiometer), mid-arm circumference (3 repeat measures), and body weight (using a certified weight scale) at clinic visits. BMI will be calculated.

10.2.7 Abdominal ultrasound

Ultrasound of the liver and spleen will be performed at Visits 1, 5, 8, and 11. Liver size, echogenicity, and presence of masses/nodules as well as spleen size will be recorded. If an ultrasound is performed as standard of care during the optional extension period, the data should be recorded in the electronic case report form (eCRF).

10.2.8 Overdose

A4250 is minimally absorbed and has a very low systemic availability. Based on toxicology data, for study purposes any dose exceeding a total of >3 mg/kg body weight of A4250 taken as a single dose or as a cumulative dose within 24 hours is defined as an overdose.

The no-adverse-effect dose level in the most sensitive species (defined as 20 mg/kg/day) in the rat 1 month toxicity study gives a human equivalent dose of approximately 194 mg/day in a 60 kg person. This dose is approximately 10-fold higher than the maximum possible dose predicted in human studies (20 mg).

The investigator/investigative staff should immediately, and not later than within 24 hours of knowledge, report an overdose in the SAE Report Form. In the event of an A4250 overdose, the patient should be monitored closely.

10.2.9 Pregnancy

If a pregnancy is discovered in a female patient enrolled in the study before the end of dosing the patient will be immediately discontinued from the study and will attend the same visits as a prematurely withdrawn patient. If the pregnancy is discovered after the end of dosing the patient will continue in the study per protocol. If a pregnancy occurs in a male patient's partner at any time during the study, the pregnancy should also be reported and followed.

Pregnancy is not considered to be an AE. However, if the patient has been dosed with the study drug, the pregnancy must be reported on the Paper Pregnancy Notification Form immediately within 24 hours after recognition to Pharmacovigilance Manager and Pharmacovigilance and Safety Services Department (please refer to [Section 10.1.3](#)). Date of exposure and as far as possible, details of the period of gestation at the time of exposure must be given.

The pregnancy should be followed up to determine outcome, including spontaneous termination, details of birth, and presence of any birth defects, congenital anomalies or newborn or maternal complication. An infant who was exposed in-utero will be followed for up to 2 years after delivery. Individual cases with an abnormal outcome in association with the study drug should be reported on an expedited basis, i.e., reported rapidly to a competent authority.

11 STATISTICAL EVALUATION

11.1 Sample Size and Power

There is no formal hypothesis testing in this open label study. Sample size for Cohort 1 was determined in Study A4250-005. For Cohort 1, patients will be enrolled following completion or participation of 12 weeks of Study A4250-005. The expected proportion of patients with at least one event, i.e., surgical bile diversion or liver transplantation or death, in untreated patients is expected to be high enough to be able to detect an improvement after A4250 treatment. For the other endpoints, mainly descriptive analyses will be performed.

The proportion of patients with at least one event (i.e., surgical bile diversion or liver transplantation or death), that can be expected in a non-treated population depends on PFIC type and age distribution of the included patients. The expected proportion of patients with events will be calculated for the study population once each patient's age and PFIC type are known, using the probability that a patient will get an event estimated from the reference population in the ongoing observational cohort study, NAtural Course and Prognosis of PFIC and Effect of Biliary Diversion (NAPPED).

As an example, if the expected proportion with at least one event is estimated to be 30% in the study population, and then if the proportion of patients with at least one event during A4250 long-term treatment are shown to be only 10% in the study, the power is approximately 89% to 96% (1-sided test, alpha=2.5%) for a confidence interval (CI) with upper boundary <30% based on a sample size of n=48 to 60. The sample size of 60 patients for Cohort 2 was estimated based on the availability of target patient population to evaluate the therapeutic benefit for those patients.

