- PFIC, Type 5 (farnesoid X receptor [FXR] deficiency): Loss of function mutations in the *NR1H4* gene encoding the farnesoid X receptor (FXR) result in PFIC5 [\[Sticova 2018\]](#). FXR is a nuclear receptor activated by bile acids and is directly involved in the expression of both BSEP and MDR3, proteins affected in PFIC2 and PFIC3, respectively [\[Gomez-Ospina 2016\]](#).
- PFIC, Type 6 (MYO5B deficiency): PFIC6 results from defects in the *Myo5B* gene that codes for the actin-associated molecular motor known as MYO5B, which is essential for the polarisation of hepatocytes as well as localising BSEP to the canalicular membrane [\[Vitale 2019\]](#).

Severe pruritus is common in children diagnosed with PFIC. Itching (and subsequent scratching) is a significant morbidity for these patients and their families [\[Suchy 2007\]](#). A more severe degree of pruritus is experienced compared to patients with other forms of liver disease and to other pruritic conditions such as atopic dermatitis [\[Murray 2011\]](#). In patients with PFIC, liver biopsy reveals canalicular cholestasis and, later, the appearance of portal fibrosis. Serum biochemistry indicates cholestasis with hyperbilirubinemia, elevated alanine aminotransferase (ALT) and aspartate aminotransferase (AST). The concentrations of bile acids in serum are very high, while serum gamma-glutamyl transferase (GGT) activity (the exception being MDR3 variants) and cholesterol [\[Hori 2010\]](#) are normal. Symptoms of portal hypertension and liver failure will develop during the course of the disease [\[Davit-Spraul 2009; Alissa 2008\]](#). Symptoms develop early; median age at onset of symptoms is 2 months, and 78% of PFIC patients present with jaundice [\[Pawlikowska 2010\]](#). The life-threatening and debilitating nature of PFIC is reflected by the fact that survival in those not resorting to surgery is 50% at 10 years of age and almost zero at 20 years of age. Approximately half of PFIC patients undergo liver transplantation [\[Davit-Spraul 2009\]](#) and treatment resistant pruritus is the leading indication for the surgical procedure partial external biliary diversion, mostly in PFIC Type 1 and 2 patients.

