7.2.3 Withdrawal of Patients

Patients/caregivers will be informed that they have the right to withdraw from the study at any time, without prejudice to their medical care, and that they are not obliged to state their reasons.

Any withdrawal, and reasons for withdrawal, must be fully documented in the eCRF and source documents and the patient followed by the investigator/investigative staff. Withdrawn patients will not be replaced.

Patients will be withdrawn in the following circumstances:

- A patient's/caregiver's desire for withdrawal for any reason
- Lost to follow-up (every effort must be made to contact the patient/caregiver; a certified letter must be sent)
- An AE which, in the opinion of the investigator, necessitates withdrawal
- Death
- A patient's/caregiver's substantial non-compliance (eDiary and study drug compliance) or protocol violation
- An investigator's opinion that continuing the patient in the study is not appropriate. The investigator may withdraw a patient at any time, if it is considered to be in the patient's best interest
- Liver transplantation

The reason and the date the patient is withdrawn from the study will be documented in the eCRF and source documents. If a patient is withdrawn from further treatment with the study drug, the investigator/investigative staff will attempt to complete all Visit 11 procedures at the time the patient is prematurely withdrawn from the study. The investigator/investigative staff will also attempt to complete all Visit 12 procedures 28 days following premature withdrawal (i.e., 28 days following the final dose of the study drug).

If a patient discontinues prior to Week 72, additional telephone contacts will be made every 3 months after the Follow-up Visit (Visit 12) up to Week 72 to gather whether or not the patient has had biliary diversion or liver transplantation, and of ongoing TEAEs at the time of discontinuation have resolved. The telephone calls will take place up until 72 weeks even if the patient has biliary diversion or liver transplant.

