11.2 Statistical Methods

11.2.1 Statistical Analysis Sets

Full Analysis Set

The full analysis set (FAS) will consist of all patients who received at least 1 dose of study drug in Study A4250-008. The FAS will be the primary analysis set for all analyses unless otherwise specified.

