11.2.2.6 Evaluation of Secondary and Exploratory Efficacy Variables

All secondary and exploratory variables listed under [Sections 9.1.2](#) and [9.1.3](#) will be analyzed descriptively for categorical and continuous data, as applicable. For continuous data, the change from baseline will be analyzed in addition to the actual visit values. For categorical data, shift tables or frequency and percentages of patients will be presented as appropriate.

Change in growth (Z-score, SD from P50 standard growth curve) will be analyzed by using one-sample T-test or Wilcoxon signed-rank test as appropriate. Change in growth (height/length for age, weight for age, BMI, and mid-arm circumference) will also be displayed using graphical presentations.

A 95% CI will be calculated for the proportion of patients experiencing surgical bile diversion or liver transplantation or death as well as for the proportion of patients experiencing surgical bile diversion or death or liver transplantation. The upper boundary will be compared to the

expected proportion of events, using the event probability estimated from the untreated reference population in an ongoing observational cohort study.

Time to first event, i.e., time to surgical bile diversion or liver transplantation or death, will be explored by descriptive statistics and Kaplan-Meier curves, which also will be used to make a comparison to the NAPPED population. The propensity score matched cohort analysis using inverse probability of treatment weights will be used to match the study patient population to the reference population based on age group and PFIC type.

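### The event comparison sets a crude proportion over all dosed patients against a reference proportion with no stated time limit, so it favours A4250 when event status to Week 72 is incomplete or the reference horizon exceeds 72 weeks

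*Protocol*

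**What the plan says.** **Observed side.** Section 11.2.2.6 states: "A 95% CI will be calculated for the proportion of patients experiencing surgical bile diversion or liver transplantation or death". The default analysis set (Section 11.2.1) is "all patients who received at least 1 dose of study drug in Study A4250-008". Section 9.1.2 evaluates these events at Weeks 24, 48 and 72. Section 11.2.2.2 says that missing observations are in general not imputed and leaves further missing-data details to the SAP.

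**Expected side.** Section 11.1 states: "The expected proportion of patients with events will be calculated for the study population once each patient's age and PFIC type are known". The probabilities come from the NAPPED observational cohort. Neither Section 11.1, Section 11.2.2.6 nor the synopsis gives a time horizon for them.

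**Rule and power.** Section 11.2.2.6 compares the upper boundary with the expected proportion. Section 11.1 works through an example with 30% expected from the reference and 10% observed on A4250. For 48 to 60 patients its result reads: "the power is approximately 89% to 96% (1-sided test, alpha=2.5%) for a confidence interval (CI) with upper boundary <30" (percent). The same section says that the study has no formal hypothesis testing.

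**Follow-up.** Under Sections 7.1.1 and 7.2.3, patients who discontinue early are telephoned every 3 months up to Week 72 about biliary diversion, liver transplantation and TEAEs that were ongoing when they stopped. Section 7.2.3 also lists as a withdrawal reason: "Lost to follow-up (every effort must be made to contact the patient/caregiver; a certified letter must be sent".

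**Second event analysis.** Section 11.2.2.6 also explores time to first event by Kaplan-Meier against NAPPED, with inverse probability weights on age group and PFIC type.

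**The concern.** The two sides of the comparison need not cover the same time. A crude proportion falls with every event that happens out of sight. A reference probability indexed only by age and PFIC type does not fall with it, and nothing in the text stops that probability at 72 weeks.

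The telephone contacts narrow the gap but leave three routes open:

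- patients who cannot be reached;
- patients who withdraw consent to contact;
- deaths after discontinuation. Death is part of the composite but is not among the items the calls are to gather. Section 10.1.2 also stops recording new AEs after permanent discontinuation.

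What is at stake is the only comparison in the protocol with a stated power and alpha, and the one that would support a claim that A4250 delays surgery, transplantation or death.

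**Working it through.** **Inputs.** From Section 11.1: reference 30%, treated 10%, n=48 to 60, one-sided alpha 2.5%. The protocol gives no rate of loss to event follow-up, so I assume a share L of 10%, 20% or 30% of all patients. I also assume a constant hazard and loss times uniform over 72 weeks.

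**Step 1: reproduce the stated power.** I use the exact (Clopper-Pearson) 95% interval.

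- n=48: 7 events give an upper bound of 27.8% and 8 give 30.2%, so success means at most 7 events. P(X≤7 | 10%) = 89.8%; P(X≤7 | 30%) = 1.1%.
- n=60: 10 events give 28.5% and 11 give 30.4%, so success means at most 10. P(X≤10 | 10%) = 96.6%; P(X≤10 | 30%) = 1.4%.

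This agrees with the stated 89% to 96%.

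**Step 2: no drug effect, share L lost.** The hazard is λ = −ln(0.7)/72 = 0.00495 per week. For a patient lost at a uniform time, the chance that an event is seen first is 1 − (1 − e^(−72λ))/(72λ) = 1 − 0.30/0.3567 = 0.159.

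The crude proportion is then 0.30(1 − L) + 0.159L = 0.30 − 0.141L. If lost patients are still observed for 4 weeks after stopping (the Visit 12 contact), 0.159 becomes 0.175 and the crude proportion is 0.30 − 0.125L. False success at n=60 is P(X≤10) at that proportion.

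| Share lost | Crude | False success, n=60 | Crude, 4 more weeks | False success, n=60 | False success, n=48 (4 more weeks) |
|---|---|---|---|---|---|
| 0% | 30.0% | 1.4% | 30.0% | 1.4% | 1.1% |
| 10% | 28.6% | 2.4% | 28.8% | 2.3% | 1.8% |
| 20% | 27.2% | 4.1% | 27.5% | 3.7% | 2.7% |
| 30% | 25.8% | 6.7% | 26.3% | 5.7% | 4.1% |

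The nominal 2.5% is passed at between 10% and 20% lost for both sample sizes.

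**Step 3: reference horizon.** Under the same hazard, a reference risk read over H weeks is 1 − 0.7^(H/72). At H=72 it is 30%. At an assumed H=104 it is 1 − 0.7^1.444 = 40.3%, with nothing changed in the patients. The protocol names no H, so this shows direction only.

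**Step 4: which matching is safe.** A natural repair is to sum the reference risk over each patient's observed time. If that time ends at the event, the sum is too small even with no loss. Event-free patients (70%) contribute 0.30 each. Patients with an event (30%) contribute on average 0.15, because 1 − S(T) is uniform between 0 and 0.30. The total is 0.7×0.30 + 0.3×0.15 = 0.210 + 0.045 = 25.5%, not 30%. The window must therefore be 72 weeks for everyone.

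**The case against.** The strongest reply is that the protocol is silent here, not wrong. No sentence says that patients of unknown status are event-free or that the reference ignores a 72-week limit. Section 9.1.2 fixes Week 72 on the observed side, and missing-data detail is left to the SAP, which was not available. The main analysis waits until the last patient completes 72 weeks. Event status is sought by telephone to Week 72. Death and transplantation are themselves recorded withdrawal reasons, Section 10.1.3 asks for an SAE form for deaths in the study period, and a call would in practice often reveal a death. A weighted Kaplan-Meier comparison is already planned, and nothing is formally tested.

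Much of this stands, and it limits the size of the point. It does not remove it. The estimator, the denominator and the inputs to the reference value are protocol text, and their default result without imputation is that unknown counts as event-free. The Kaplan-Meier comparison is exploratory and is not the quantity whose upper bound is compared.

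Three stronger readings are tempting but unsupported.

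- *The bias is certain.* It depends on a loss rate the protocol does not give, and it is zero if status is complete and the reference stops at 72 weeks.
- *The power is wrong.* It reproduces. Counting lost patients as event-free would raise the chance of success, not lower it.
- *The expected proportion is about four times too high.* A reader might infer this from Section 5.2.1, "survival in those not resorting to surgery is 50% at 10 years of age and almost zero at 20 years of age". A constant hazard matched to age 10 gives 1 − 0.5^(1.38/10) = 9.1% over 72 weeks against 1 − 0.5^(7/10) = 38.4% from age 3 to 10. But no section says the reference runs to age 10, the sentence concerns survival without surgery and not the composite, and that hazard leaves 0.5² = 25% alive at 20, which contradicts the same sentence.

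**Conclusion.** The point holds in conditional form. As written, the upper-bound comparison is not matched in time, and any mismatch from lost patients or a reference horizon beyond 72 weeks works in favour of A4250.

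From loss alone the effect is modest: about 1.4 percentage points of the crude proportion per 10% of patients lost, or 1.25 points with 4 further weeks of observation. False success at n=60 reaches about 4% at 20% lost and 6% to 7% at 30% lost. These figures rest on a 30% risk, a constant hazard, uniform loss and assumed loss shares. They also assume that lost patients have the same risk as the others.

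The effect of the horizon cannot be sized from the document. It needs no loss at all to operate, so it should be settled explicitly.

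**What to change.** 1. In Section 11.2.2.6, base the upper-bound comparison on the Kaplan-Meier 72-week cumulative incidence of the composite with its 95% CI, censoring each patient at the last known event status. Keep the crude proportion as a description.
2. In Sections 11.1 and 11.2.2.6, define the expected proportion as the average over patients of the reference 72-week risk, 1 − S(a + 72 weeks)/S(a), where a is age at entry and S is the reference event-free curve for the patient's PFIC type. Use 72 weeks for every patient, not observed time ending at the event (Step 4).
3. Add vital status to the items gathered at the existing telephone contacts in Sections 7.1.1 and 7.2.3.

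The cost is mainly wording plus one question per call, since the Kaplan-Meier analysis and the use of the reference cohort are already planned. The CI becomes slightly wider and the expected proportion may come out lower. The Kaplan-Meier estimate relies on non-informative censoring, so the number of patients with unknown status at Week 72, and the reasons, should be reported beside it.
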